15.1.3.7 Pneumothorax

The incidence of pneumothorax is much lower than that of bleeding. The risk of pneumothorax is not related to the size of the biopsy forceps. Routine postoperative expiratory chest X-ray should be performed. In most subjects, even if pneumothorax occurs, it is usually mild and does not require chest tube insertion for closed thoracic drainage. However, for subjects with hypoxia and/or tension pneumothorax, chest tube placement is necessary for closed thoracic drainage.

15.2 OTHER POTENTIAL RISKS DURING THE REGEND001 CELL THERAPY PROCESS

Initial treatments conducted in class A tertiary hospital in Shanghai and Chongqing demonstrated good safety. However, due to the relatively small number of overall cases, potential risks or unexpected situations are hereby disclosed.

15.2.1 MULTIPLE ORGAN DYSFUNCTION SYNDROME (MODS)

Due to the rich capillary network in the lungs, there is a possibility that REGEND001 cells, if present in excessive amounts in the bloodstream, may cause multiple organ dysfunction. However, the REGEND001 cell therapy in this project is administered via the trachea, which closely resembles human physiology and clinical practice. By directly reaching the lung interstitium, it bypasses the multiple barriers involved in intravenous administration, such as the endothelium, interstitium, and basement membrane, significantly reducing the risk of multi-organ distribution to less than 0.01% and minimizing the possibility of organ dysfunction.

15.2.2 LOCAL TUMOR FORMATION

Currently, there have been no reports of tumor formation from REGEND001 cells in animal experiments or in the clinical research conducted earlier. The term "local tumor formation" mainly refers to tumors appearing in the bronchial airway, most likely caused by cellular accumulation, particularly from natural apoptosis. The treatment methods for intrabronchial tumors include

fiberoptic bronchoscopy for intraluminal removal or surgical intervention. If the tumor is malignant, further chemotherapy or radiotherapy may be required after surgery.

15.2.3 OTHER POTENTIAL COMPLICATIONS

No clinical study-related complications were observed during the previous clinical research of REGEND001 cell therapy. Common complications during REGEND001 cell therapy mainly arise from fiberoptic bronchoscopy procedures, which were elaborated in the preceding text. However, it is challenging to estimate other potential complications at present. When unknown complications occur, corresponding treatment principles usually involve symptomatic support, surgical interventions, and consultation with relevant departments.

15.2.4 ALLOGENEIC TRANSPLANTATION

Existing operating techniques ensure that cells from one subject will not be transplanted into another subject's body. Measures include the use of QR code scanning technology during cell harvesting, transportation, and

processing for unique batch numbering and separate production for each subject.

If allogeneic transplantation of REGEND001 cells is discovered early, whole-lung lavage can be performed to remove the cells. If discovered later, follow-up observation is sufficient as allogeneic REGEND001 cells are difficult to engraft and survive.

15.2.5 ACUTE EXACERBATION OF DISEASE

Acute IPF exacerbation refers to a sudden deterioration of the condition, worsened breathlessness, and decreased lung function without any clear cause, leading to respiratory failure or even death.

The diagnostic criteria for acute IPF exacerbation are as follows:

(1) History of IPF, or current clinical, imaging, and/or histological findings consistent with the diagnosis of IPF. If the previous diagnosis was not IPF based on the diagnostic criteria, current imaging and/or lung tissue pathology should indicate usual interstitial pneumonia pattern.

(2) Exacerbation of dyspnea or worsening of lung function within the past 30 days, not explainable by other causes.

(3) High-resolution computed tomography (HRCT) of the chest showing bilateral reticular or honeycomb patterns consistent with usual interstitial pneumonia, along with new ground-glass opacities and/or consolidations. If there is no prior contrast-enhanced HRCT, "new pulmonary imaging findings" can be disregarded.

(4) Absence of evidence for lung infection in tracheal secretions or bronchoalveolar lavage, including routine bacterial, opportunistic pathogen, and common viral examinations.

(5) Exclusion of other causes, including left heart failure, pulmonary embolism, and acute lung injury caused by other reasons. Causes of acute lung injury may include sepsis, aspiration, trauma, reperfusion pulmonary edema, pulmonary contusion, fat embolism, inhalation injury, cardiac bypass surgery, drug toxicity, acute

pancreatitis, transfusion of blood products, and cell transplantation.

When clinical data is incomplete or does not meet all five diagnostic criteria mentioned above, it is defined as suspected acute IPF exacerbation. Histopathologically, it is typically characterized by the coexistence of usual interstitial pneumonia (UIP) and diffuse alveolar damage (DAD), which may present with organizing pneumonia and significant fibroblast foci. Acute exacerbation leads to a worsening of lung function in IPF subjects, shortened survival time, poor treatment response, and high mortality rate.

Acute exacerbation of IPF is severe, with a high mortality rate. Clinically, pulse corticosteroid therapy (methylprednisolone 500-1000 mg/day) or high-dose corticosteroid treatment (prednisone $\geq 1 \text{ mg}\cdot\text{kg}^{-1}\cdot\text{day}^{-1}$) is still used. Although there is currently no consensus on the dosage, administration route, and duration of corticosteroid use, treatment can also include immunosuppressants, such as cyclophosphamide and cyclosporine A. Oxygen therapy, mechanical ventilation,

and symptomatic treatment are the main therapeutic measures for patients with acute exacerbation of IPF.

16 DATA MANAGEMENT

Electronic Data Capture (EDC) technology is increasingly being utilized in clinical trials. It differs from traditional paper-based data collection methods and offers advantages such as real-time data entry, immediate identification of data errors, accelerated research progress, and improved data quality. As a result, regulatory authorities in various countries encourage the adoption of EDC technology in clinical trials to ensure data quality. The main functions of EDC are as follows.

16.1 ECRF CONSTRUCTION

EDC systems are capable of generating electronic case report forms (eCRFs) that comply with the clinical trial protocol.

16.2 DATA STORAGE AND AUDIT TRAIL

Once data is input into the EDC system, it retains an audit trail for all data modifications, preventing deletion or modification of audit trails.

16.3 LOGICAL CHECKS

One of the key advantages of EDC is its ability to perform real-time automatic logical checks on data entry, such as data value ranges and logical relationships. The specific checks are outlined in the data verification plan tailored to each clinical trial. EDC systems are equipped with logic check modules.

16.4 DATA QUERY MANAGEMENT

EDC systems have modules for generating, issuing, and closing data queries. Authorized data managers and/or clinical monitors can issue data queries to clinical research sites. The sites are responsible for confirming, explaining, or correcting the queried data. Authorized data managers can decide whether to close the query based on the response, or re-query data that does not meet

requirements. All data query records should be preserved for reference.

16.5 SOURCE DATA VERIFICATION CONFIRMATION

Source data verification confirmation is essential for ensuring the authenticity and integrity of clinical data. Clinical monitors are responsible for conducting source data verification on data stored in the EDC system. Source data confirmation can be accomplished using the data query function in the system.

16.6 ELECTRONIC SIGNATURES

EDC systems have electronic signature functionality for all electronic records that require electronic signatures, including the generation, modification, maintenance, archiving, recovery, or transmission of any form of electronic forms. Electronic signatures can be implemented using login passwords and system-generated authorization codes. The association and legal equivalence between electronic signatures and handwritten signatures should be declared and confirmed

by authorized users before implementing electronic signatures, and authorized electronic signatures have the same legal effect as their written handwritten signatures.

16.7 DATABASE LOCKING

EDC systems have a locking function to prevent clean data that has been verified or confirmed from being altered. Once clinical data cleaning is completed, the EDC system can lock the database.

16.8 DATA STORAGE AND EXPORT

EDC systems can store, export, or convert data into formats that meet clinical trial audit requirements and drug evaluation requirements.

For more information on Electronic Data Capture (EDC), refer to the "Guiding Principles for Electronic Data Capture Technology in Drug Clinical Trials."

17 STATISTICAL ANALYSES

17.1 SAMPLE SIZE DETERMINATION

The sample size for this study is planned to be between 15 to 24 cases.

17.2 DEFINITION AND SELECTION OF ANALYSIS SETS

Full Analysis Set (FAS): This set includes all enrolled cases that have received the study drug. FAS is used for reporting demographic data and baseline characteristics.

Per-Protocol Set (PPS): The PPS comprises cases that meet the inclusion criteria, do not meet the exclusion criteria, and have completed the treatment protocol. In other words, it includes cases that adhered to the trial protocol, completed Case Report Forms (CRFs) or electronic Case Report Forms (eCRFs), and are suitable for analysis (PP analysis). PP analysis is primarily used for efficacy assessment.

Safety Set (SS): The SS consists of actual data with safety indicators recorded from the initiation of fiberoptic bronchial cell collection. Safety-related missing values

should not be carried forward. The SS may exclude certain cases for evaluation, such as cases exceeding the age inclusion criteria, but it does not include cases where safety assessments cannot be made due to the use of prohibited drugs. SS is used for safety evaluation analysis.

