5.2 MANAGEMENT OF INELIGIBLE SUBJECTS DURING CELL CULTURING

In the time interval between subject enrollment and cell treatment (usually 4-8 weeks), if a subject who initially met the inclusion criteria becomes unsuitable for cell therapy (e.g., acute exacerbation of the condition, occurrence of severe complications), the subject's physical condition will be assessed by the researchers. If it is anticipated that the subject's condition can meet the standards for receiving cell transplantation after relevant interventions and observations, the cell therapy preparation work will be temporarily suspended. In such cases, there is no need to obtain new

cells, and the cells that have already been cultured or partially cultured will be cryopreserved according to the relevant regulations of the production facility. Once the subject is medically cleared, they can directly proceed to the trial, reschedule the treatment time, and use the cells for treatment after cell recovery, culturing, and testing. If, based on the researcher's assessment, the subject is deemed unsuitable to continue participating in the study (such as an anticipated lack of short-term improvement in the physical condition), the subject will be considered a screening failure, and their cells will be destroyed. Before the completion of the entire study, a subject can undergo a maximum of two baseline assessments to verify the inclusion criteria. If the subject fails to meet the criteria for cell therapy during the second baseline assessment, the subject will be withdrawn from the trial, and the cells will be destroyed or cryopreserved for long-term storage if requested by the subject. If, until the end of the study, the subject is unable to meet the inclusion criteria, the subject will be withdrawn from the study, and the cells will be destroyed or cryopreserved for long-term storage if requested by the subject.

Considerations regarding the standards or scope of pre-treatment examinations for subjects undergoing cell therapy primarily involve the researcher's further verification of the inclusion criteria. If the subject still meets the selection

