8.2 SECONDARY OUTCOME MEASURES

- Incidence of complication related to bronchoscopy within 24 weeks after treatment.

- Changes in lung diffusing capacity for single-breath carbon monoxide (DLCO-sb) compared to baseline at 4-, 12-, and 24-weeks post-treatment.
- Changes in Forced Vital Capacity (FVC) compared to baseline at 4-, 12-, and 24-weeks post-treatment.
- Changes in the ratio of diffusing capacity for carbon monoxide/ the alveolar volume (DLCO/VA) compared to baseline at 4-, 12-, and 24-weeks post-treatment.
- Changes in 6-minute-walk test (6MWT) compared to baseline at 4-, 12-, and 24-weeks post-treatment.
- Changes in the St. George's Respiratory Questionnaire (SGRQ) scale compared to baseline at 4-, 12-, and 24-weeks post-treatment.
- Changes in imaging of lung by high-resolution computed tomography (HR-CT) compared to baseline at 24 weeks post-treatment.
- Frequency and severity of IPF exacerbation events within 24 weeks after treatment.
- Number of cases of participants with abnormal Blood routine results within 24 weeks post-treatment.
- Number of cases of participants with abnormal Urine routine results within 24 weeks post-treatment.

- Number of cases of participants with abnormal Blood biochemistry results within 24 weeks post-treatment.
- Number of cases of participants with abnormal 12-lead Electrocardiogram (ECG) results within 24 weeks post-treatment.
- Changes in tumor markers (Cytokeratin 19 fragment (CYFRA21-1), Neuron-specific enolase (NSE), Squamous cell carcinoma antigen (SCC), Carcinoembryonic antigen (CEA)) compared to baseline at 4-, 12-, and 24-weeks post-treatment.

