11 ADVERSE EVENTS

11.1 DEFINITION OF ADVERSE EVENTS

Adverse Events (AE): Refers to all adverse medical events that occur in subjects after receiving investigational drug. These events can manifest as symptoms, signs, diseases, or abnormal laboratory findings, but may not necessarily have a causal relationship with the investigational drug. They include the following situations:

(1) Exacerbation of pre-existing medical conditions/diseases (including worsening of symptoms, signs, and laboratory abnormalities) that were present before entering the clinical trial.

(2) Newly occurring AEs: Any newly occurring adverse medical condition (including symptoms, signs, and newly diagnosed diseases).

(3) Clinically significant abnormal laboratory values or results that are not caused by accompanying diseases.

Adverse Drug Reactions (ADR): Refers to any harmful or unexpected reactions related to the investigational drug that occur during the clinical trial. There must be at least a reasonable possibility of a causal relationship between the investigational drug and the adverse reactions, which means that the correlation cannot be ruled out.

Significant Adverse Events: Refers to any AE, other than Serious Adverse Events (SAE), that requires specific medical interventions (such as drug discontinuation, dose reduction, and symptomatic treatment), and results in significant hematological or other laboratory abnormalities.

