11.2 COLLECTION AND RECORDING OF ADVERSE EVENTS

Monitoring of Adverse Events (AE) will be conducted throughout the entire study, and it is the responsibility of the investigators to record all AEs observed during the study period. Any adverse medical events occurring from the initiation of autologous cell collection until the end of follow-up, regardless of severity or causal relationship with the investigational drug, must be documented in the medical records. Detailed documentation of the following information is required for all AEs:

- **AE Description:** Describe the AE using medical terminology rather than the language reported by the subjects. If applicable, include symptoms, signs, abnormal laboratory findings, and diagnosis. If the same AE occurs more than once in a subject and the subject has recovered between the two events, each occurrence should be recorded separately.

- **AE Onset Date:** The date when the subject first experienced the AE or when symptoms related to the AE appeared. If the AE is a clinically significant abnormal laboratory finding or test result, the date of sampling should be recorded.
- **AE Outcome Date:** The date of resolution of the AE or when symptoms related to the AE improved. If the AE is still ongoing, the outcome date does not need to be filled.
- **Severity of AE.**
- **Causal Relationship between AE and the investigational drug.**
- **Actions Taken:** (1) Actions taken with regard to the investigational drug: continued use, discontinued use, treatment completed, not applicable; (2) Actions taken regarding the AE: none, medication treatment, non-drug treatment.
- **Outcome of AE:** Disappeared, recovery with sequelae, improvement, stable, aggravated, death, subject refusal for follow-up or lost to follow-up, unknow.

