17.3.2 SAFETY EVALUATION

Adverse events (AEs) will be recorded after the first bronchoscopy collection and following the second bronchoscopy treatment. The description of AEs after the first bronchoscopy collection and the analysis of AEs after the second bronchoscopy treatment are as follows:

(1) Calculation of the incidence and severity of cell therapy-related adverse events (AEs) for each group.

(2) Calculation of the incidence of bronchoscopy-related complications for each group.

(3) Calculation of the mean, standard deviation, median, and interquartile range for the dynamic changes of each lung tumor biomarker in all groups.

(4) Presentation of the cross-tabulation of routine safety check abnormalities (complete blood count, urinalysis, blood biochemistry, electrolytes, electrocardiogram) between baseline and each visit.

(5) Recording the frequency and severity of acute IPF exacerbations

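### The Safety Set, which carries the primary endpoint, may leave out dosed patients at discretion, and no all-dosed denominator is named for the by-group adverse event rate

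*Protocol*

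**What the plan says.** **Analysis sets (protocol 17.2).** The Full Analysis Set is everyone enrolled who received the product; its stated use is demographics and baseline characteristics. The Per-Protocol Set serves mainly efficacy. Of the Safety Set the protocol says: "The SS consists of actual data with safety indicators recorded from the initiation of fiberoptic bronchial cell collection". It continues "The SS may exclude certain cases for evaluation, such as cases exceeding the age inclusion criteria", and in the same sentence, on prohibited medication, "it does not include cases where safety assessments cannot be made due to the use of prohibited drugs". The Safety Set is then assigned to the safety analysis.

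**Primary endpoint.** Sections 6 and 8.1 define it as therapy-related adverse events over the 24 weeks following treatment. Section 17.3.2 plans: "Calculation of the incidence and severity of cell therapy-related adverse events (AEs) for each group".

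**Subjects collected but not dosed.** Cell collection precedes dosing by about 4 to 8 weeks (1.4). If a subject becomes unsuitable in that interval without expected recovery, "the subject will be considered a screening failure, and their cells will be destroyed" (5.2). A second failed culture also ends participation (5.3).

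**Bronchoscopy complications and event windows.** Section 8.2 lists "Incidence of complication related to bronchoscopy within 24 weeks after treatment", and section 6 uses the same window. Section 11.1 defines an adverse event thus: "Refers to all adverse medical events that occur in subjects after receiving investigational drug". Section 11.2 requires documentation of "Any adverse medical events occurring from the initiation of autologous cell collection until the end of follow-up". The lead-in to 17.3.2 pairs a description of events after the collection bronchoscopy with an analysis of events after the treatment bronchoscopy, and the item on bronchoscopy complications stands beneath it.

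**The concern.** In a first dose-escalation study whose primary question is safety, the set that yields the primary rate should contain every exposed patient. Exceeding the age limit (50 to 75, section 2.2) is an eligibility deviation. It does not undo the exposure, and such a patient's toxicity still informs about the dose.

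The wording has three weaknesses. The exclusion is permissive rather than defined. Age is given only as an example, so the list is open. Nothing says who decides or when, and the trial is open-label (1.1), so the decision can be taken with the event already known. The prohibited-drug clause gives no criterion for when an assessment is impossible.

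The one unrestricted set of dosed patients, the Full Analysis Set, is not assigned to safety. A secondary purpose of the trial (section 1) is to recommend doses for later studies, and a false zero in one dose group would feed directly into that recommendation.

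**Working it through.** **1. The plan's own figure.** Group sizes come from section 1.3: three groups of 3 to 6 and a fourth of 6.
- Minimum: 3 + 3 + 3 + 6 = 15.
- Maximum: 6 + 6 + 6 + 6 = 24.

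Both agree with the 15 to 24 in sections 1.7 and 17.1. The protocol states no event rate, no number of over-age patients and no number collected but undosed. Everything below therefore uses assumed counts with the protocol's group sizes.

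**2. Excluding one dosed patient who had the only related event.** The rate is x/n before and (x − 1)/(n − 1) after. Intervals are exact 95% Clopper-Pearson, with lower limit the 0.025 quantile of Beta(x, n − x + 1) and upper limit the 0.975 quantile of Beta(x + 1, n − x). The lower limit is 0 when x = 0.

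| Dosed in group | All dosed | After exclusion |
|---|---|---|
| 6 | 1/6 = 16.7% (0.4 to 64.1%) | 0/5 = 0% (0 to 52.2%) |
| 3 | 1/3 = 33.3% (0.8 to 90.6%) | 0/2 = 0% (0 to 84.2%) |

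The intervals are wide either way. What changes is that an observed related event disappears from the group's table.

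**3. Counting u undosed subjects in the denominator (one possible reading).** The rate becomes x/(n + u), with u assumed between 0 and 6.
- One group, 2 events in 6 dosed: 2/6 = 33.3%; u = 1 gives 2/7 = 28.6%; u = 6 gives 2/12 = 16.7%.
- Whole trial, 3 events: 3/24 = 12.5% becomes 3/30 = 10.0% with u = 6; 3/15 = 20.0% becomes 3/21 = 14.3% with u = 6.

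If every collected subject is dosed, u = 0 and nothing changes.

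**4. Windows side by side.**

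| Text | Starts at |
|---|---|
| Bronchoscopy-complication endpoint (6, 8.2) | Treatment |
| Adverse event definition (11.1) | Receipt of product |
| Adverse event recording (11.2) | Cell collection |
| Safety Set data (17.2) | Cell collection |
| Safety analysis lead-in (17.3.2) | Both bronchoscopies, collection described and treatment analysed |

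Each dosed patient has two planned bronchoscopies, and the endpoint window as worded reaches one of them. The time it omits is 4/(24 + 4) = 14% to 8/(24 + 8) = 25% of the span from collection to week 24. The events in that span are recorded, so this is a conflict of wording.

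**The case against.** The strongest reply is that the exclusion sentence is garbled. Its two halves are joined as a contrast, which makes little sense if both remove patients, so over-age cases may have been meant to stay in. Eligibility is also checked at V1 and again at V3, so a dosed over-age patient should be rare. Both points are fair. They lower the chance of harm and cast doubt on the intent, but the text as it stands permits removal and needs correction on either reading.

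Four stronger readings are tempting, and the protocol does not support them.
- *All patients who took a prohibited drug are dropped.* The clause covers only those whose safety cannot be assessed because of the drug.
- *Starting the Safety Set at collection is itself an error.* Collection is an invasive study procedure, and 11.2 requires recording from that point. The weakness is one set serving two periods.
- *The by-group rate is certainly diluted by undosed subjects.* The primary endpoint runs from treatment, dose groups are described by the administration received (1.3), and patients formally join only after the V3 recheck (1.4). Section 5.2, however, places enrolment before culture is complete, and 17.2 names no dosed-only denominator for safety. Dilution is therefore possible but not stated.
- *The collection bronchoscopy goes unreported.* Section 17.3.2 covers events after both procedures, and the flowchart's adverse event row begins at V2.

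The escalation rules in 1.3 and 1.6 do not refer to the Safety Set, so escalation decisions are unaffected. An analysis plan that is not shown may add detail, but the exclusion itself is stated in the protocol.

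**Conclusion.** The Safety Set definition is wrong as written. It allows a dosed patient to be left out of the primary safety analysis for an eligibility deviation, with an open list of reasons and no fixed decision point. At 3 to 6 patients per group, one such exclusion can move a dose group's observed rate from 16.7% or 33.3% to zero. That size assumes the excluded patient had the group's only related event; if no dosed patient is excluded, there is no effect.

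The missing dosed-only denominator is an ambiguity, and it matters only if some collected subjects are never dosed. The bronchoscopy-complication window and the adverse event definition are a secondary inconsistency, with no loss of data.

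**What to change.** - Delete both exclusions from the Safety Set in 17.2.
- Define a treated set: everyone who received any REGEND001, grouped by dose actually received. Use it for the primary endpoint and all by-dose post-treatment safety tables.
- Define a collection set: everyone who started a collection bronchoscopy, including those later classed as screening failures or lost to culture failure. Use it for the pre-treatment period.
- Show eligibility deviations and prohibited medication as flags in the listings, with a sensitivity table if wanted.
- Reconcile the complication window in 6 and 8.2 with 11.2 and 17.3.2 by reporting complications separately for the collection bronchoscopy (including any repeat sampling under 5.3) and the transplantation bronchoscopy.
- Align the adverse event definition in 11.1 with the recording period in 11.2. The serious adverse event text in 12.1 and 12.2 has the same mismatch.

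The cost is revised wording and one more table; the data are already recorded from V2. Reported rates may look slightly less favourable.
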